7.6 DOSE ESCALATION

There will be 4 weeks between dosing of subjects within a cohort. For the first cohort, the allowance of four weeks between dosing of subjects provides time for safety review from five time points (days 1, 2, 7, 14 and 30) prior to dosing of the next subject and time for review of the safety analysis of all the subjects within a cohort by the investigators and the DSMB.

This timeline will also provide time for review of any clinically significant improvement based on the 6MWT data. [REDACTED]

[REDACTED]

The investigators will confer with the IRB, DSMB, and FDA/CBER on all grade – 3 or higher adverse events that are possibly, probably, or definitely related to the study agent before continuing enrollment. Based on the outcome of the safety and efficacy analysis at the end of each cohort decisions will be made to proceed with dose escalation for the following cohort.

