Semen samples will be requested on day 90 from all sexually active males age 18 years or older, for PCR analysis for vector genomes. This interval is based on selecting a date post-gene transfer that is longer than the 70 days required from the beginning of the first meiotic division to the completion of spermatogenesis. As mature sperm spend an additional 5-15 days in the epididymis, a date three months after gene transfer is therefore optimal to look for any possible germ line incorporation. Testing will continue until 2 consecutive negative samples are obtained.

Blood samples will be obtained for immune studies at days 7, 14, 30, 60, 90, 180 post gene transfer and 9, 12, 18, and 24 months; this will include testing for binding antibody to rAAVrh74, as well as ELISpot to detect T cell response to capsid antigens. GGT will be measured at 45 and 75 days post gene transfer to assess delayed sub-clinical hepatitis.

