Note: There will be a flexibility of +/- 7 or +/- 21 working days as outlined for each of the planned study visits including screening to adjust the schedule to any unanticipated event. There will also be potential additions to care based on best medical management if the need arises including additional fluids to restore blood volume.

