7.3 DOSE SELECTION

There will be three cohorts of LGMD2D subjects [Cohorts 1A (n=1), 1B (n=3), and 2 (n=3)] with dosing permitted by toxicology- biodistribution study and predicted by pre-clinical studies in non-human primates. The trial will start with low dose gene transfer (1×10^{12} vg/kg per limb); the first patient (Cohort 1A) enrolled will receive a single unilateral infusion to one lower extremity. The same dose will be delivered to three subjects (Cohort 1B) infused to both lower extremities. The total vector genomes dosed for each subject will be adjusted by rounding to the closest 5 kg per the discretion of the PI or designated co-investigator. The subjects in Cohort 2 (n=3) will receive a total dose of 3×10^{12} vg/kg per limb delivered to both extremities. Table 6.3 below shows dosing for the clinical trial based on weights from clinic subjects eligible for the clinical gene transfer trial.

Patient wt (kg):		20-29	30-39	40-49	50 - 59	60 - 69	70 - 79	80 - 89	90 - 99	100 - 109	110 - 119	120 - 129
Cohort	Dose/quad	Total Dose / Patient (total vector genomes)										
(1)	LD 1e12vg/kg/limb	4e13	6e13	8e13	1.0e14	1.2e14	1.4e14	1.6e14	1.8e14	2.0e14	2.2e14	2.4e14
(2)	HD 3e12vg/kg/limb	1.2e14	1.8e14	2.4e14	3.0e14	3.6e14	4.2e14	4.8e14	5.4e14	6e14	6.6e14	7.2e14

Reference Table: Total Dose (vg) per subject based on bodyweight (kg)

* LD = low dose; HD = high dose

If safety data is obtained at low dose, the third cohort of three additional subjects will receive the next escalating dose (6×10^{12} vg/kg total dose) split between the two limbs.

Subjects within a cohort will be entered at intervals of approximately 4-6 weeks. Additional time will be allowed to review the biopsy results of the first subject in the first cohort prior to

dose escalation to the next cohort. Intervals within subjects in the second cohort can be reduced base on safety observed in first cohort.

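### Protocol 7.6 counts the Day 30 safety review among those possible before the next subject is dosed, but a four-week gap ends on Day 28 and no visible rule makes dosing wait

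*Protocol*

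**What the plan says.** Section 7.6 of the protocol opens with a flat interval: "There will be 4 weeks between dosing of subjects within a cohort". For the first cohort it adds that "four weeks between dosing of subjects provides time for safety review from five time points (days 1, 2, 7, 14 and 30"), and it places that review "prior to dosing of the next subject and time for review of the safety analysis of all the subjects within a cohort".

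Section 7.3 words the interval more loosely: "Subjects within a cohort will be entered at intervals of approximately 4-6 weeks". It then adds: "Intervals within subjects in the second cohort can be reduced base on safety observed in first cohort".

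Table 2 in section 6.8 puts the infusion on Day 0 and gives the Day 30 visit a window of ±21 days. The note below it reads "There will be a flexibility of +/- 7 or +/- 21 working days as outlined for each of the planned study visits", and explains that the allowance is there to absorb unanticipated events.

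Section 6.4 schedules an examination, safety labs and immune studies at Day 30: "Blood samples will be obtained for immune studies at days 7, 14, 30, 60, 90, 180 post gene transfer". It also provides that "GGT will be measured at 45 and 75 days post gene transfer to assess delayed sub-clinical hepatitis".

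**The concern.** The sentence in 7.6 describes a property that the interval does not have. A reader, or a DSMB member, would take from it that each subject's one-month results are in hand before the next infusion. At the stated spacing they need not be.

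The visit matters. Table 2 schedules nothing between Day 14 and Day 30. Day 30 brings the full safety panel (GGT, bilirubin, platelets, CK and creatinine among others) and the ELISpot. Under section 6.3, prednisone starts the day before gene transfer and runs for about one month, so Day 30 falls about when that cover ends or is tapered. The same section plans for GGT rises after 30 days, and section 6.4 looks for delayed hepatitis later still. Section 11.3.1 describes the product as being given to humans for the first time.

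What is at stake is whether an early sign in one subject is seen before the next subject receives a one-time infusion that cannot be withdrawn.

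**Working it through.** **Inputs.** Interval: 4 weeks (7.6), or about 4–6 weeks (7.3). Stated review points: Days 1, 2, 7, 14 and 30 (7.6). Infusion on Day 0; windows of ±7 days for visits up to Day 14 and ±21 days from Day 30 onward (Table 2). Cohort sizes 1, 3 and 3 (synopsis).

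**1. The plan's own figure: five time points within four weeks.**
4 × 7 = 28 days. Days 1, 2, 7 and 14 fall before Day 28; Day 30 does not. The count is 4 of 5, and 30 − 28 = 2 days late.

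**2. Day numbering does not rescue it.** SAP section 5.1 calls the infusion day Day 1, so four weeks later is Day 29. Even a visit labelled Day 30 on that scale comes 1 day after it.

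**3. The other four points hold with their windows.** The latest of them, Day 14, can run to 14 + 7 = Day 21. In working days (Monday–Friday, holidays ignored) it can run to Day 23–25. Both are before Day 28.

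**4. The looser interval in 7.3, with the Day 30 visit on its nominal day.**

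| Gap | Days | Days left after Day 30 |
|---|---|---|
| 4 weeks | 28 | 28 − 30 = −2 |
| 5 weeks | 35 | 35 − 30 = +5 |
| 6 weeks | 42 | 42 − 30 = +12 |

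A gap of 5 or 6 weeks works if the visit is on time. It is permitted, not required.

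**5. The window, as an outer bound.** In calendar days: 30 − 21 = Day 9 to 30 + 21 = Day 51. The late edge is 51 − 28 = 23 days after a four-week dosing and 51 − 42 = 9 days after a six-week one. In working days the late edge is Day 59–61, depending on the weekday of infusion, which is 31–33 days after Day 28. The early side works the other way: a visit brought forward to before Day 28 could be reviewed in time, but nothing visible requires that.

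**6. Decisions affected.** Within-cohort gaps: Cohort 1A, 1 − 1 = 0; Cohort 1B, 3 − 1 = 2; Cohort 2, 3 − 1 = 2. The five-point sentence is limited to the first cohort. If that means the low-dose group, it concerns the 2 gaps in Cohort 1B. If it means Cohort 1A alone, there is no within-cohort gap for it to govern.

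**The case against.** The strongest reply is that this is loose wording. Four weeks stands for about a month, 7.3 allows up to six weeks, and 7.6 plainly intends the Day 30 review to come first. A five-week gap does that with 5 days to spare. The intent is clear enough, but the flat four-week statement in 7.6 contradicts it, and the choice of a longer gap is left open.

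Several further replies limit how far the point can be taken.

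- **Window.** A reader might infer from ±21 days that a Day 30 visit on Day 51 is routine. The note to Table 2 ties the allowance to unanticipated events, so the figures in step 5 are extremes, not expected delays.
- **Day 14 data alone.** A reader might infer that the next subject is dosed on Day 14 labs and nothing later. Section 6.3 mentions weekly GGT and immune responses in setting the duration of prednisone. That may apply only when prednisone is extended, and it is not the full panel, but it prevents so strong a claim.
- **No minimum in the second cohort.** A reader might infer that 7.3 removes any floor for the high-dose subjects. The flat 4 weeks in 7.6 can be read as that floor. The term second cohort is also unclear, since 7.3 itself calls the high-dose group the third.
- **Other safeguards.** Section 6.6 stops on one related Grade III or two related Grade II toxicities. Section 7.5 halts enrollment for a related Grade 3 event. Section 6.7 shares data with the DSMB as gathered, and section 8.3 reports serious events and dose-limiting toxicities within 48 hours. These are real protections, but they cannot act on a Day 30 sample not yet drawn.
- **Redaction.** Text directly after the timing sentences in 7.6 is blacked out and may hold a gate. One may say that no rule is visible, not that none exists. A hidden rule would supply the protection but would not make the visible sentence correct.

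**Conclusion.** The point stands in a limited form. At the interval 7.6 states, 4 of the 5 review points are secured and Day 30 is not. The nominal shortfall is 2 days, and it grows if the contingency window is used. Section 7.3 permits a sufficient gap without requiring one, and no unredacted text makes the next dosing wait for Day 30 results.

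The documents do not show that a subject would be dosed without any recent data, or that all four within-cohort gaps contradict the sentence. As worded it reaches 2 of them at most, on the low-dose reading of the first cohort. Section 11.3.2.11 reports events in subjects of this study, so some had already been dosed; how many dosing decisions an amendment could still affect is unknown.

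The conclusion rests on Day 0 being the infusion day and on four weeks meaning 28 days. It should be corrected, because the remedy is one sentence and the subject is the safety of the next infusion.

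**What to change.** In 7.6, replace the fixed four weeks with a condition, for example: *The next subject in a cohort will not be dosed until the preceding subject's Day 30 examination and safety labs, drawn on or after Day 28, have been reviewed (about 5 weeks).* Apply it to Cohorts 1B and 2. In 7.3, add that any reduced interval remains subject to this review. If the redacted text already contains such a rule, only the interval wording needs aligning.

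**Cost.** No scheduled visit, test or subject is added. The documents give no turnaround time. Assuming 3–7 days for results and review after a visit on Day 30, the gap becomes 30 + 3 = 33 to 30 + 7 = 37 days, within the 28–42 days of 7.3. That is 5–9 days more than 28 per gap, or 20–36 days if all four gaps were still to come.

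If the visit is late, the gap lengthens day for day. At the calendar late edge it would be 51 + 3 = 54 to 51 + 7 = 58 days, beyond six weeks. A visit held before Day 28 would need its examination and labs repeated to satisfy the condition. Narrowing the Day 30 window would limit both, but that is the sponsor's choice and the correction does not depend on it.

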7.7 CONCOMITANT MEDICATIONS/THERAPIES

Prescribed and over the counter medications used in the prior two weeks will be recorded at the baseline visit and changes in these medications will be recorded during each subsequent medical history. The PI will encourage participants to maintain the medication and supplements they are on at enrollment through the course of the study. Subjects on aspirin or drugs that could affect coagulation will continue their medication as indicated. Several investigations show that preoperative aspirin ingestion and intravenous heparin therapy can be administered safely without concerns about the risk of postoperative bleeding and should not lead to modification or cessation of such therapy.¹³⁻¹⁵

8.0 ADVERSE EVENT MONITORING AND REPORTING

8.1 DEFINITION OF AN ADVERSE EVENT

As stated above (6.2.7.4) this protocol will follow the final regulations issued by the Food and Drug Administration addressing the safety reporting requirements for investigational new drug applications (INDs) found in 21 CFR part 312 and for bioavailability and bioequivalence studies found in 21 CFR part 320. "Safety Reporting Requirements for INDs and BA/BE Studies".

<http://www.fda.gov/downloads/Drugs/GuidanceComplianceRegulatoryInformation/Guidances/UCM227351.pdf>

Adverse Events will be collected throughout the study from enrollment to last follow up visit.

Adverse Event (AE): Adverse event means any untoward medical occurrence associated with the use of a drug in humans, whether or not considered drug related.

Adverse events will be graded by the investigator accordingly:

Grade 1 Mild; asymptomatic or mild symptoms; clinical or diagnostic observations only; intervention not indicated.

Grade 2 Moderate; minimal, local or noninvasive intervention indicated; limiting age-appropriate instrumental ADL*.

Grade 3 Severe or medically significant but not immediately life-threatening; hospitalization or prolongation of hospitalization indicated; disabling; limiting self care ADL**.

Grade 4 Life-threatening consequences; urgent intervention indicated.

Grade 5 Death related to AE.

A Semi-colon indicates 'or' within the description of the grade.

A single dash (-) indicates a grade is not available.

Activities of Daily Living (ADL)

*Instrumental ADL refer to preparing meals, shopping for groceries or clothes, using the telephone, managing money, etc.

**Self care ADL refer to bathing, dressing and undressing, feeding self, using the toilet, taking medications, and not bedridden.

Association or relatedness to the study agent, study procedures and the subject's pre-existing disease will be graded as follows: 5 = unrelated, 4 = unlikely, 3 = possibly, 2 = probably, and 1 = definitely related.

Adverse reaction: An adverse reaction means any adverse event caused by a drug. Adverse reactions are a subset of all suspected adverse reactions for which there is reason to conclude that the drug caused the event.

Suspected adverse reaction (21 CFR 312.32(a)) Suspected adverse reaction means any adverse event for which there is a reasonable possibility that the drug caused the adverse event. For the purposes of IND safety reporting, 'reasonable possibility' means there is evidence to suggest a causal relationship between the drug and the adverse event. A suspected adverse reaction implies a lesser degree of certainty about causality than adverse reaction, which means any adverse event caused by a drug.

Serious adverse event (SAE)

An adverse event or suspected adverse reaction is considered "serious" if, in the view of either the investigator or sponsor, it results in any of the following outcomes: Death, a life-threatening adverse event, inpatient hospitalization or prolongation of existing hospitalization, a persistent or significant incapacity or substantial disruption of the ability to conduct normal life functions, or a congenital anomaly/birth defect. Important medical events that may not result in death, be life-threatening, or require hospitalization may be considered serious when, based upon

appropriate medical judgment, they may jeopardize the subject and may require medical or surgical intervention to prevent one of the outcomes listed in this definition. Examples of such medical events include allergic bronchospasm requiring intensive treatment in an emergency room or at home, blood dyscrasias or convulsions that do not result in inpatient hospitalization, or the development of drug dependency or drug abuse.

To reiterate, an SAE is an event in categories graded 3, 4, and 5.

Grade 3 Severe or medically significant but not immediately life-threatening; hospitalization or prolongation of hospitalization indicated; disabling; limiting self care ADL**.

Grade 4 Life-threatening consequences; urgent intervention indicated.

Grade 5 Death related to AE.

Life-threatening (21 CFR 312.32(a)) An adverse event or suspected adverse reaction is considered "life-threatening" if, in the view of either the investigator or sponsor, its occurrence places the subject at immediate risk of death. It does not include an adverse event or suspected adverse reaction that, had it occurred in a more severe form, might have caused death.

The PI will fulfill the reporting responsibilities to FDA/ OBA on behalf of Nationwide Children's Hospital using the web-based Adverse Event reporting system (GeMCRIS).

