7.4 DOSE LIMITING TOXICITY

In reporting adverse events we will follow the final regulations issued by the Food and Drug Administration addressing the safety reporting requirements for investigational new drug applications (INDs) found in 21 CFR part 312 and for bioavailability and bioequivalence studies found in 21 CFR part 320. "Safety Reporting Requirements for INDs and BA/BE Studies".

<http://www.fda.gov/downloads/Drugs/GuidanceComplianceRegulatoryInformation/Guidances/UCM227351.pdf>

The classification for adverse events to be used is the following:

- 1 Mild adverse event; did not require treatment
- 2 Moderate adverse event; resolved with treatment
- 3 Severe adverse event; inability to carry on normal activities; required professional medical attention
- 4 Life-threatening or permanently disabling adverse event
- 5 Fatal adverse event

In this grading system, “**severe**” is not equivalent to *seriousness*.

The definitions to be employed will follow the final regulations issued by the FDA in September 2010 “Safety Reporting Requirements for INDs and BA/BE Studies”, and described in section 7.4 of this protocol.

Dose limiting toxicity (DLT) is defined as any adverse event that is possibly, probably, or definitely related to the study agent. This would include any grade 3 event according to the classification given above.

Study enrollment will be halted by the investigators when any subject experiences a Grade 3, or higher adverse event toxicity that is possibly, probably, or definitely related to the study drug.

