8.3 SAFETY REPORTING

The investigator or his designee will report all serious and unexpected adverse events to the IRB, IBCSC, CBER, FDA, OBA, NIH, and DSMB according to regulatory requirements described as follows:

NIAMS and DSMB:

All Serious Adverse Events (SAEs) and Dose Limiting Toxicities (DLTs) will be reported to the **NIAMS** and the **DSMB** through KAI within **48 hours** of notification, regardless of relatedness to the clinical trial. KAI Research, Inc. serves as the NIAMS Executive Secretary.

FDA/NIH OBA/IRB

Any serious adverse event that is fatal or life-threatening, that is unexpected, and associated with the use of the gene transfer product will be reported by the study investigator concurrently to the **FDA/NIH OBA/IRB** as soon as possible, but not later than **7 calendar days** after the sponsor's initial receipt of the information.

Serious adverse events that are unexpected and associated with the use of the gene transfer product, but are not fatal or life threatening, will be reported concurrently to the **FDA/NIH OBA/IRB** as soon as possible, but not later than **15 calendar days** after the sponsor's initial receipt of the information. Changes in this schedule will be permitted only where, under the **FDA IND** regulations [21 CFR 312(c) (3)], changes in this reporting schedule have been approved by the FDA and are reflected in the protocol.

If, after further evaluation, an adverse event initially considered not to be associated with the use of the gene transfer product is subsequently determined to be associated, then the event will be reported concurrently to the **FDA/NIH OBA/IRB** as soon as possible, but in no case later than 15 calendar days after the determination is made.

FOLLOW-UP

Relevant additional clinical and laboratory data will become available following the initial serious adverse event report. Relevant follow-up information to an IND safety report will be submitted concurrently to the **FDA/NIH OBA/IRB/ NIAMS** and the **DSMB** through **KAI** as soon as the information is available and will be identified as such, i.e., "Follow-up IND Safety Report."

If a serious adverse event occurs after the end of a clinical trial and is determined to be associated with the use of the gene transfer product, that event will be reported concurrently to the **FDA/NIH OBA/IRB/ NIAMS** and the **DSMB** through **KAI** within 15 calendar days of the determination.

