6.6.2 Adverse Events

Adverse events (AEs) will be coded using the Medical Dictionary for Regulatory Activities (MedDRA) [Version 22.0].

AEs will be graded by the Investigator as follows:

- Grade 1: Mild; asymptomatic or mild symptoms; clinical or diagnostic observations only; intervention not indicated
- Grade 2: Moderate; minimal, local or noninvasive intervention indicated; limiting age-appropriate instrumental activities of daily living (ADL)*
- Grade 3: Severe or medically significant but not immediately life-threatening; hospitalization or prolongation of hospitalization indicated; disabling; limiting self-care ADL**
- Grade 4: Life-threatening consequences; urgent intervention indicated

Sponsor Protocol ID: 9004-101 Covance Study ID: 000000209191

Grade 5: Death related to AE

A Semi-colon indicates 'or' within the description of the grade.

- *Instrumental ADL refer to preparing meals, shopping for groceries or clothes, using the telephone, managing money, etc.
- **Self-care ADL refer to bathing, dressing and undressing, feeding self, using the toilet, taking medications, and not bedridden.

The relationship between an AE and study drug is assessed as definite, probable, possible, unlikely, or not related. A treatment-related AE is an AE considered by the investigator as definitely, possibly, or probably related to study drug or with unknown/missing relationship to study drug.

All AE data recorded in eCRF will be listed. In addition, a listing of serious AEs (SAEs) will be produced.

Treatment-emergent AEs (TEAEs) will be summarized by cohort and overall. TEAEs are AEs that occur or worsen in severity on or after gene transfer. AEs with missing start date will be considered as TEAEs.

TEAEs will be summarized by cohort and overall. An overview table will summarize the number and percentage of subjects with at least one of the following TEAEs, where subjects with more than one TEAE in a particular category are counted only once in that category:

- Any TEAE
- TEAE by maximum severity grade
- Treatment-related TEAE
- Any treatment-emergent SAE (TESAE)
- Treatment-related TESAE
- TESAE leading to death

The number of total TEAEs will be also included in the overview table.

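### Protocol 8.1 gives two serious adverse event rules that do not agree, one by outcome and one by grade, and the SAP does not say which one defines a TESAE.

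*Protocol*

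**What the plan says.** Protocol 8.1 calls an event serious if "it results in any of the following outcomes: Death, a life-threatening adverse event, inpatient hospitalization or prolongation of existing hospitalization", and continues with significant incapacity or disruption of normal life, "or a congenital anomaly/birth defect", and important medical events identified by medical judgment. The same section then says "To reiterate, an SAE is an event in categories graded 3, 4, and 5" and repeats the descriptions of Grades 3 to 5.

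Protocol 7.4, which has its own differently worded severity scale, says that severe, on that scale, "is not equivalent to *seriousness".

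Protocol 8.3 ties reporting to seriousness: "All Serious Adverse Events (SAEs) and Dose Limiting Toxicities (DLTs) will be reported to the" NIAMS and the DSMB within 48 hours, whatever the relatedness. Unexpected and associated SAEs go to the FDA, NIH OBA and IRB within 15 days, or within 7 days if they are also fatal or life-threatening.

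SAP 6.6.2 plans an SAE listing and an overview table that includes "Any treatment-emergent SAE (TESAE"). It grades events on the Protocol 8.1 scale, reports maximum grade separately and takes adverse event data from the eCRF. It gives no criteria for seriousness.

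**The concern.** Safety is the primary objective, and TESAEs are among its main summaries. A serious flag is useful because it says something that the severity grade does not. If sites set the flag by grade, the number of subjects with any TESAE equals the number with a maximum grade of 3 or more. The TESAE row then repeats the severity row, and an event that is serious by outcome but graded low is left out. If sites set it by outcome, the row means something else. A reader of the tables cannot tell which meaning applies.

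The question can arise in practice. Protocol 11.3.2.11 reports myoglobinuria from rhabdomyolysis in subjects of this study and tells subjects with symptoms to alert the investigator or go to an emergency room. An episode treated there without admission is the kind of event for which grade and outcome can give different flags. The documents do not give the grades or flags of those cases.

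**Working it through.** The plan states no figure on this point, so the check compares the two rules on the protocol's own text. A note under the Protocol 8.1 scale says that semicolons mean *or*, so one element is enough to reach a grade.

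| Event | Outcome rule | Grade rule |
|---|---|---|
| Severe only; no admission, no incapacity (Grade 3) | Not serious unless judged an important medical event | SAE |
| Limits self-care briefly (Grade 3) | Serious only if the incapacity or disruption is judged significant | SAE |
| Needs urgent intervention without immediate risk of death (Grade 4) | Not life-threatening as Protocol 8.1 defines it; may be an important medical event | SAE |
| Congenital anomaly | Serious | Not named in any grade; SAE only if graded 3 or more |
| Important medical event graded 1 or 2 | Serious | Not an SAE |
| Hospital stay prolonged | Serious | SAE, because Grade 3 names prolongation |
| Death | Serious | SAE (Grade 5) |

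The first three rows show where the grade rule is too wide, the next two where it is too narrow, and the last two where the rules agree.

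The outputs that depend on the flag are:

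- **SAP 6.6.2:** the SAE listing, and the overview rows for any TESAE and treatment-related TESAE. The row for TESAEs leading to death is unaffected.
- **SAP 6.6.2, tables by SOC and PT:** those for TESAEs and treatment-related TESAEs. The death table is unaffected.
- **SAP 6.6.2.1:** the TESAE tables for important potential risks and for other risks.
- **Protocol 8.3:** the 48-hour route is the most exposed, because it takes all SAEs. The 15-day route is exposed only for unexpected and associated events. The 7-day route is largely unaffected, because it also needs a fatal or life-threatening event and Protocol 8.1 defines life-threatening separately.
- **Protocol 7.4, 7.5 and 12.1:** the enrollment halt is triggered by related events of Grade 3 or higher. It does not use the SAE definition.

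The effect of one subject follows from the cohort sizes in SAP 2.3 (1, 3 and 3; total 7) and the cohort denominators in SAP 6.1. Moving one subject into or out of a row changes it by 100/n percentage points:

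- Cohort 1A: 100/1 = 100 points
- Cohort 1B or Cohort 2: 100/3 = 33.3 points
- Overall: 100/7 = 14.3 points

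This is the arithmetic of any single change in so small a trial and does not estimate how many subjects are misclassified. The rows count subjects with at least one event, so a reclassified event moves a subject only if that subject has no other event in the row.

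**The case against.** The strongest reply is that the outcome definition is given in full and that Protocol 7.4 and 8.1 commit the trial to the FDA safety-reporting regulations. On this view the grade sentence is loose shorthand. The SAP does not adopt it, and a SAP that takes seriousness from the eCRF makes no error by not re-deriving it. That is fair as far as it goes. A reader might infer that the TESAE counts and expedited reports use the wrong rule, but the documents do not support this: they contain both rules and do not say which one sites followed.

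Several further replies also stand:

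- A reader might think that the grade rule misses a low-grade event that prolongs the overnight stay. On the Protocol 8.1 scale, prolongation is itself a Grade 3 criterion, so the example fails.
- Grade 3 also covers medically significant events, which narrows the gap for important medical events. The discrepancy is mainly over-inclusion, the cautious direction for safety.
- The conflict with Protocol 7.4 is indirect. The statement there concerns that section's scale, whose Grade 3 reads "Severe adverse event; inability to carry on normal activities; required professional medical attention" and does not name hospital admission. The SAE sentence uses the Protocol 8.1 scale, which does.
- The 48-hour route also takes dose-limiting toxicities, so many related Grade 3 events would reach NIAMS and the DSMB under either rule.
- With seven subjects, every adverse event is listed, so no event disappears from view.

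These replies limit the consequences but do not make the two rules equivalent. The grade sentence is stated without qualification, and neither document says which rule takes precedence.

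**Conclusion.** The concern holds as an unresolved contradiction in a definition that feeds primary-objective outputs. Protocol 8.1 states two SAE rules that classify some events differently, and the SAP tabulates TESAEs without naming the rule behind the flag. The listing, rows, tables and two reporting routes identified above may differ by rule; death outputs, the 7-day route and the enrollment halt are largely unaffected.

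The number of affected events cannot be derived and could be zero. The conclusion assumes that the grade sentence is read on the Protocol 8.1 scale, whose descriptions follow it, and that no eCRF completion guideline outside these documents already settles the matter.

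**What to change.** 1. **Protocol 8.1.** Reconcile the passages by removing the sentence that equates SAEs with Grades 3 to 5, and the grade list after it, so that seriousness follows the outcome-based definition alone. Protocol 8.3 also uses the SAE term for an infusion in progress; how that clinical instruction should read is outside this point.
2. **SAP 6.6.2.** State that TESAEs use the eCRF serious flag, set by the outcome-based definition in Protocol 8.1.
3. **Before the tables are run.** Check all recorded adverse events of every grade in the seven subjects for disagreement between grade and outcome criteria, and resolve each one with the investigator. A check limited to Grade 3 or higher and hospitalised events would miss the non-hospitalised Grade 1 and 2 events that the grade rule can leave out.

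The cost is one deleted sentence and list, one added SAP sentence, and a single pass through seven subjects' records. Protocol 11.6.3 planned enrollment to end in December 2017. With 24 months of follow-up that reaches December 2019, and the SAP is dated 25 April 2022. If those dates held, a protocol amendment comes too late to change site reporting, and steps 2 and 3 matter most.
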